### Section 7.3.2.3.1 Pre and post bronchodilator FEV1

**Rationale for change:** To add “morning long-acting anticholinergic (LAMA)”

#### Revised text

Only pre-bronchodilator assessments are required at Visit 1. Both pre- bronchodilator and post-bronchodilator assessments are required from Visit 2 onwards. At each visit, spirometry assessments should be performed at the same time of day ( $\pm$  1 hour) as the assessment performed at Visit 2 (the baseline assessment). Subjects should withhold short-acting beta-2-agonists (SABAs) for  $\geq$  6 hours and LABAs for  $\geq$  12 hours and their dose of long-acting anticholinergic (LAMA) prior to the clinic visit. if possible.

### Section 7.4.7 Clinical Safety Laboratory Assessments

#### Table 5 Protocol Required Safety Laboratory Assessments

**Rationale for change:** to correct a typographical error in appendix No.

#### Revised text

Laboratory Assessments	Parameters			
Haematology	Platelet Count	RBC Indices:	WBC count with Differential:	
	RBC Count	MCV	Neutrophils	
	Hemoglobin	MCH	Lymphocytes	
	Hematocrit		Monocytes	
			Eosinophils	
			Basophils	
Clinical Chemistry 	BUN	Potassium	AST (SGOT)	Total and direct bilirubin
	Creatinine	Sodium	ALT (SGPT)	Total Protein
	Glucose	Calcium	Alkaline phosphatase	Albumin
Other Screening Tests	
 
Hepatitis B (HBsAg)
 
Hepatitis C (Hep C antibody)
 
FSH and estradiol (as needed in women of non-child bearing potential only)
 
Alcohol and drug screen (to include at minimum: amphetamines, barbiturates, cocaine, opiates, cannabinoids and benzodiazepines)
 
Urine hCG Pregnancy test (as needed for women of child bearing potential)
 
			

## NOTES :

1. Details of Liver Chemistry Stopping Criteria and Required Actions and Follow-Up Assessments after liver stopping or monitoring event are given in Section 5.5.3 and Appendix 2 Appendix 5
2. Local urine testing will be standard for the protocol unless serum testing is required by local regulation or ethics committee.

**Section 7.5 Biomarker(s)/Pharmacodynamic Markers**

**Rationale for change:** To clarify that eosinophil count is not blinded

**Revised text**

Blood eosinophil counts will be recorded as part of the standard haematological assessments performed at the visits specified in the Time and Events Schedule (Section 7.1). ~~From Visit 2 onwards, blood eosinophil counts will not be communicated to investigators, in order not to bias the investigator assessment of patient response to treatment.~~ Additional blood samples for exploratory biomarkers of type 2 helper T cells (Th2) response, will be collected at Visits 1, 2, 4 and 10. Details on collecting and handling of biomarker samples can be found in the SRM.

**Section 12.7 Appendix 7 Sub-section 12.7.2 last bullet point****Revised text**

**Rationale for change:** To correct the Appendix No as it was a typographical error

**Revised text:** Refer to Appendix 2 Appendix 5 for the required liver chemistry follow-up instructions

1. REPORTING & ANALYSIS PLAN SYNOPSIS

Overview	Key Elements of the RAP
Purpose	
 This reporting and analysis plan (RAP) details all planned analyses and outputs required for the final Clinical Study Report (CSR) of study 204471. The critical components RAP was completed on the 10th February 2016. This document represents the final RAP and will be provided to the study team members to convey the content of the Statistical Analysis Complete (SAC) deliverable.
Protocol	
 This RAP is based on protocol amendment 1 (Dated: 23-MAR-2016) for study 204471 (GSK Document No.: 2015N243304_01) and the latest version of the electronic Case Report Form (eCRF) [eCRF Version 2.1].
Primary Objective	
 To determine in a pragmatic setting whether there is an improvement in asthma control, from the beginning to the end of the study, when directly switched from omalizumab to mepolizumab in subjects with a severe eosinophilic asthma phenotype not optimally controlled on omalizumab.
Primary Endpoint	
 Mean change from baseline in ACQ-5 score at Week 32
Study Design	
 An open label, single arm, 32-week treatment, multi-center study in subjects with severe eosinophilic asthma not optimally controlled with current omalizumab treatment who are switched from omalizumab to mepolizumab 100mg administered subcutaneously (SC) every 4 weeks. Approximately 120 subjects are expected to be treated with open label mepolizumab.
Planned Analyses	
 No interim analysis of data is planned for this study. A complete analysis in accordance with all study objectives and endpoints will be performed after all subjects have completed the study. Decisions regarding the analyses, specified in this RAP document, will be made prior to Database Freeze of the study data.
Analysis Populations	
 The 'All Subjects Enrolled' population will be used to summarise Screen and run-in failures. The 'Intent-to-Treat' population will be used as the primary population to summarise the study population, and to evaluate efficacy, safety and PD/Biomarkers. The 'Per Protocol' population will also be used as a supporting population to evaluate efficacy. Subjects excluded will have protocol deviations considered to potentially have an effect on efficacy.
Hypothesis	
 As there is no control arm within this study, comparisons in ACQ score will be made back to baseline. The potential of a 'placebo effect' within the mepolizumab treated subjects was considered when the study was designed and was estimated as an improvement of -0.55 from baseline in ACQ score, based on placebo subjects within historical mepolizumab severe asthma studies. However, when only previous Xolair users were considered, an improvement of -0.11 from baseline in ACQ score was observed. This study is designed to test the superiority of mepolizumab 100 mg SC

Overview	Key Elements of the RAP
	treatment vs. baseline. Improvements will also be assessed against the historical 'placebo effects' estimated from previous mepolizumab studies. Significance tests will be performed at the two-sided 5% alpha level (one-sided 2.5%).
Primary Analyses	
 ACQ-5 score will be analysed using a mixed models repeated measures analyses allowing for covariates of region, use of baseline maintenance oral corticosteroids therapy (OCS vs no OCS), exacerbations in the year prior to the study (as an ordinal variable), and visit (including baseline visit).
Secondary Analyses	
 SGRQ score will be analysed using a mixed models repeated measures analysis as for ACQ-5. Frequency of clinically significant asthma exacerbations will be analysed using a negative binomial regression analysis Blood eosinophil count will be analysed using a mixed model repeated measures analysis after log transformation
Safety Analysis	
 Safety data including adverse events, vital signs, clinical laboratory, electrocardiogram (ECG), and immunogenicity data will be summarised descriptively.

2. SUMMARY OF KEY PROTOCOL INFORMATION

2.1. Changes to the Protocol Defined Statistical Analysis Plan

Statistical analysis changes to the originally planned statistical analysis specified in the protocol amendment 1 (Dated: 23-MAR-2016) (GSK Document No.: [2015N243304_01](#)) are outlined in [Table 1](#).

Table 1 Changes to Protocol Defined Statistical Analysis Plan

Protocol	Reporting & Analysis Plan	Rational for Changes
Statistical Analysis Plan	Statistical Analysis Plan	

 Analysis of change from baseline in ACQ, SQRQ scores will be performed using a mixed models repeated measures (MMRM) analysis, allowing for covariates of baseline ACQ score, region, baseline maintenance OCS therapy, exacerbations in the year prior to the study (as an ordinal variable), visit and an interaction term for visit by baseline ACQ score. Clinically significant exacerbations will be analyzed using a generalized linear model with covariates for region, baseline maintenance OCS therapy and number of exacerbations in the year prior to the study (as an ordinal variable). 	
 Baseline values will be included as a data point in the analysis, and there will be no covariate adjustment made in the model. The change from the baseline at Visit X will be calculated by: Estimated Score at Visit X minus Estimated Score at Baseline. Clinically significant exacerbations will be examined using a generalized estimating equation (GEE) with no adjustments for covariates. 	
 This is a single treatment arm study and comparisons are being made directly to the baseline values. Generalised estimating equations (GEEs) will compare the on-treatment exacerbation rate to the rate within the 12 months prior to study.

[figure not shown]

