6.	Controller Medication: Current treatment with an additional controller medication, besides ICS, for at least 3 months or a documented failure in the past 12 months of an additional controller medication for at least 3 successive months. [e.g., long-acting beta-2-agonist (LABA), leukotriene receptor antagonist (LTRA), long-acting anticholinergic (tiotropium bromide), or theophylline.]
7.	Asthma symptoms not optimally controlled: An ACQ-5 score of $\geq 1.5$ recorded at Visit 1.
8.	Omalizumab Treatment: Receiving omalizumab, based on weight and IgE levels, for at least the 4 months prior to Visit 1.
9.	Exacerbation history: Previously confirmed history of two or more exacerbations requiring treatment with systemic corticosteroids (intramuscular, intravenous, or oral) in the 12 months prior to Visit 1 despite the use of high-dose ICS. For subjects receiving omalizumab for $\geq 8$ months, at least one exacerbation must have occurred while on omalizumab treatment. For subjects receiving maintenance oral corticosteroids, the corticosteroid treatment for the exacerbations must have been a two-fold dose increase or greater.

SEX
10. Male or eligible Female
Females:
a. Non-reproductive potential defined as:

 
• Pre-menopausal females with one of the following:           
 
• Documented tubal ligation
 
• Documented hysteroscopic tubal occlusion procedure with follow-up confirmation of bilateral tubal occlusion
 
• Hysterectomy
 
• Documented Bilateral Oophorectomy
 
 
 
• Postmenopausal defined as 12 months of spontaneous amenorrhea [in questionable cases a blood sample with simultaneous follicle stimulating hormone (FSH) and estradiol levels consistent with menopause (refer to laboratory reference ranges for confirmatory levels)]. Females on hormone
 

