### **7.3.2.4. Clinically Significant Asthma Exacerbation**

***Clinically significant exacerbations of asthma are defined by:***

Worsening of asthma which requires use of systemic corticosteroidsand/or hospitalisation and/or Emergency Department (ED) visits.

*For all subjects, i.v. or oral steroid (e.g., prednisone) for at least 3 days or a single IM CS dose is required. For subjects on maintenance systemic corticosteroids, at least double the existing maintenance dose for at least 3 days is required.*

Exacerbation data will be included in the analysis from Visit 2 until Exit Visit (Week 32) approximately 4 weeks after the last dose of study treatment. For those subjects that stop study treatment early or withdraw early from the study altogether, the time period for collection of exacerbation data will be from Visit 2 until no greater than approximately 4 weeks post-last-dose of mepolizumab. For consistency, exacerbations separated by less than 7 days will be treated as a continuation of the same exacerbation.

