8.1.2. Secondary Efficacy Statistical Analyses

Secondary Statistical Analyses
Secondary Endpoint(s)

 Mean change from baseline in SGRQ at Week 32
Model Specification

 See Primary Efficacy Statistical Analysis, Section 7.1.2
Model Checking & Diagnostics

 Refer to Appendix 11: Model Checking and Diagnostics for Statistical Analyses.
Model Results Presentation

 Adjusted means and the corresponding 95% confidence intervals will be presented by visit. The estimated adjusted means will be presented using the observed marginal distribution of the sample covariates (OM option in LSMEANS statement). The Kenward and Roger method for approximating the denominator degrees of freedom and correcting for bias in the estimated variance-covariance of the fixed effects will be used (DDMF=KR). An unstructured covariance structure for the R matrix will be used by specifying 'type=UN' on the REPEATED line. Change from the baseline at each Visit X will be calculated by (Estimated Score at Visit X minus Estimated Score at Baseline) and the corresponding 95% confidence intervals. Adjusted means at each visit will also be presented. Plots of LS means change from baseline in SGRQ Score and 95% confidence intervals from the model will be generated by visit.
On-treatment Phase

 See Primary Efficacy Statistical Analysis, Section 7.1.2

Secondary Statistical Analyses
Secondary Endpoint(s)

 Frequency of clinically significant asthma exacerbations over 32 week treatment Frequency of exacerbations requiring ED visit/hospitalization during the 32 week treatment period Frequency of exacerbations requiring hospitalization during the 32 week treatment period
Model Specification

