
 The frequency of clinically significant exacerbations will be analysed using Negative Binomial regression via generalised estimating equations with a covariate of time period (pre-, post-mepolizumab). Exacerbations separated by less than 7 days will be treated as a continuation of the same exacerbation. The pre-mepolizumab exacerbation values (in the 12 months prior) will be obtained at screening, while the post-mepolizumab exacerbation values will be observed during the study. The variance of the mean estimate will be corrected for within-subject correlation. The logarithm of time on treatment will be used as an offset variable.
Model Checking & Diagnostics

 Refer to Appendix 11: Model Checking and Diagnostics for Statistical Analyses.

Secondary Statistical Analyses
Model Results Presentation

 Adjusted exacerbation rate and the corresponding 95% confidence interval will be presented.
On-treatment Phase

 All subjects in the ITT population will be included within this analysis. All data collected up to and including Week 32 from patients, including those who have discontinued study treatment, will be included in the analysis. An On-Treatment “de jure” analysis will also be performed which does not consider any data collected following treatment discontinuation (see On-Treatment definition within Section 10.4).
Sensitivity and Supportive Statistical Analyses

 The On-Treatment “de jure” analysis will be also performed with a subset of patients who were on omalizumab for more than 12 months.

Secondary Statistical Analyses
Secondary Endpoint(s)

 Ratio to baseline in blood eosinophil count at week 32
Model Specification

 See Primary Efficacy Statistical Analysis, Section 7.1.2 A log-transformation will be applied to blood eosinophil count data prior to analysis. If a blood eosinophil count of zero is reported, it will be imputed with half of the lowest possible blood eosinophil count, where applicable, prior to log transforming the data (Note: this imputation has typically been $0.5 * 0.01 \text{ GI/L} = 0.005 \text{ GI/L}$ for previous mepolizumab studies).
Model Checking & Diagnostics

 Refer to Appendix 11: Model Checking and Diagnostics for Statistical Analyses..

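### The exacerbation comparison uses the same 12 months in which entry required at least two events, so it includes regression to the mean

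*SAP*

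**What the plan says.** Protocol 9.4.2 planned a negative binomial model of the on-study count only, with region, baseline maintenance OCS and prior exacerbations as covariates. It had no pre-period.

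SAP 2.1 (Table 1) replaces this with a GEE without covariate adjustment and gives the reason: "Generalised estimating equations (GEEs) will compare the on-treatment exacerbation rate to the rate within the 12 months prior to study". SAP 8.1.2 specifies negative binomial regression by GEE with period (pre or post mepolizumab) as the covariate, a variance correction for within-subject correlation, and log treatment time as the offset. On the source of the comparator it says: "The pre-mepolizumab exacerbation values (in the 12 months prior) will be obtained at screening". The stated output is: "Adjusted exacerbation rate and the corresponding 95% confidence interval will be presented". The one supportive subset is "a subset of patients who were on omalizumab for more than 12 months", analysed on-treatment. The same block also lists "Frequency of exacerbations requiring ED visit/hospitalization during the 32 week treatment period" and a hospitalisation endpoint.

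Protocol 5.1, criterion 9, sets the entry rule on that count: a subject needs at least two confirmed exacerbations, each treated with systemic corticosteroids, during the year before Visit 1.

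For ACQ-5, the SAP gives benchmarks for change without active drug: -0.55 and, in previous Xolair users, -0.11 (SAP 1, 2.4 and 7.1.3). It gives none for exacerbations.

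**The concern.** Subjects enter because their count in one particular year was at least two. Some of them have a usual rate that high, and others had an unlucky year. If individual rates are stable, the next period's expected rate is lower than the selected year's rate even when nothing has changed. Using the selected year as the comparator builds that fall into the post/pre contrast, in the direction that favours mepolizumab.

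A lower on-study rate would naturally be read as fewer exacerbations because of the switch. Part or all of the difference could come from the entry rule. The sponsor allows for non-drug change in ACQ-5, but the text of neither document mentions it for exacerbations, where eligibility is set on the outcome itself.

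**Working it through.** **The plan's own figures.** The documents give no rate, dispersion, rate ratio or power for exacerbations. Their only sample-size case is ACQ-5, and it reproduces. With 120 × 0.85 = 102 evaluable subjects, SE = 0.96/√102 = 0.0951. The threshold is -0.55 - 1.96 × 0.0951 = -0.736 (stated -0.74), and power at -0.86 is 90.3% (stated 90%). It does not bear on this endpoint.

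**Inputs from the documents.** Comparator window 12 months (SAP 2.1, 8.1.2); entry threshold of at least 2 in that window (Protocol 5.1); 120 treated, 15% withdrawal (Protocol 9.2.1); 32 weeks.

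**Assumptions.** Each subject has a constant true rate drawn from a gamma distribution with mean μ per year and dispersion a (k = 1/a). Counts are Poisson given that rate. There is no effect of any kind. Grid: μ = 1.5 to 4, a = 0.25 to 1.5.

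**Expected ratio in closed form.**
- P(0) = (k/(k+μ))^k and P(1) = k × μ/(k+μ) × P(0)
- Pre rate among those admitted: E[Y | Y≥2] = (μ - P(1)) / (1 - P(0) - P(1))
- Post rate among those admitted: (k + E[Y | Y≥2]) / (k/μ + 1)

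Worked case, μ = 2, a = 0.5 (k = 2):
- P(0) = (2/4)² = 0.25; P(1) = 2 × 0.5 × 0.25 = 0.25
- pre = (2 - 0.25)/0.5 = 3.50
- post = (2 + 3.50)/(2/2 + 1) = 2.75
- ratio = 2.75/3.50 = 0.786, an apparent 21% reduction with no effect

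The same formulas at the two ends of the grid:

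| μ, a | pre | post | ratio |
|---|---|---|---|
| 1.5, 0.25 | 2.88 | 1.88 | 0.65 |
| 4, 1.5 | 6.74 | 6.35 | 0.94 |

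With no entry threshold the ratio is exactly 1. Within this grid the bias shrinks as the rate or the dispersion rises.

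**How often a CI would exclude 1.** Simulation at 16 grid points, 4,000 trials of 120 subjects each. Follow-up was 32/52 year, or uniform between 4 and 32 weeks for the 15% who withdraw. The log rate ratio used a robust within-subject variance.

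| μ, a | mean ratio | 95% CI below 1 |
|---|---|---|
| 1.5, 0.25 | 0.652 | 99.7% |
| 2, 0.5 | 0.784 | 83.7% |
| 3, 1.0 | 0.899 | 32.9% |
| 4, 1.5 | 0.941 | 17.2% |
| no entry rule, whole grid | 0.998 to 1.002 | 2.4% to 3.3% |

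**Do the planned features remove it?**
- *Variance correction.* It changes the standard error and leaves the expected pre-period rate as it was.
- *Covariates.* SAP 10.10.1 lists region, prior exacerbations and OCS for all model-based analyses, while Table 1 says this model has none. If they are added, a term that acts equally on both periods does not remove a shift between periods. Fitting the negative binomial GEE with them at five grid points (300 trials each) gave ratios of 0.67 to 0.97, with the CI below 1 in 7% to 99%.
- *Long-term omalizumab subset.* These subjects also had to meet criterion 9 in the same window.

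**The case against.** **The main fix is already planned.** The objective is to determine frequency, the stated output is a rate with 95% CI (SAP 8.1.1 Table 5 note 4; SAP 8.1.2), and no ratio or test is named. This stands, and it limits the point to wording. However, the SAP's stated reason for changing the model is the comparison itself, and the period covariate produces it.

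**The size depends on the chosen grid.** This also stands. With rates of 1 to 4 per year and dispersion 0 to 2, the ratio runs from 0.42 to 0.95. At 6 per year with dispersion 0.5 to 1.5 it is about 0.965. The direction does not depend on the grid; the size does.

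**Stronger readings that a reader might infer, and that the documents do not support:**
- *Stopping omalizumab is a further bias.* The objective concerns a direct switch from omalizumab to mepolizumab (Protocol 3; SAP 2.2), so any effect of stopping belongs to the switch being studied.
- *Time before omalizumab contaminates the pre-period and is ignored.* Criterion 8 asks only for "Receiving omalizumab, based on weight and IgE levels, for at least the 4 months prior to Visit 1", so some prior years may include such time. The planned subset (SAP 8.1.2, Table 2.21) addresses it.
- *The prior-year count uses a looser event definition.* On study, "For all subjects, i.v. or oral steroid (e.g., prednisone) for at least 3 days or a single IM CS dose is required". Criterion 9 does not state that duration, but it does require at least a two-fold dose increase for subjects on maintenance OCS. It is also an eligibility rule and is not shown to define the pre-period count. The definition is unstated, which differs from being shown to differ.
- *The outputs carry no caveat.* Only the text can be checked. The table shells are separate documents (SAP 10.14).

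**Conclusion.** The point holds as a defect in the specified comparison. The selection window and the comparator window are the same, so the post/pre contrast includes regression to the mean in favour of mepolizumab, and nothing in the plan takes it out. Under the stated assumptions and no effect, the ratio is about 0.65 to 0.94 and its 95% CI lies below 1 in about 17% to over 99% of trials, against 2% to 3% without the entry rule. These figures are an illustration. They rest on stable individual rates and on assumed means and dispersions, and they describe an implied contrast, not a planned decision rule.

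The on-study annualised rate does not use the prior year as a comparator, so this problem does not affect it as a description of frequency. Nor does the point show that a true benefit is absent. The ED/hospitalisation and hospitalisation endpoints are affected only if they use the same model. They are listed in the same block, but the model sentence names clinically significant exacerbations alone. This is a secondary endpoint with a wording-level remedy, so the change should be made but does not touch the primary analysis.

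**What to change.** In SAP 2.1 and 8.1.2:

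1. Make the on-study annualised rate with 95% CI the main result. It is already planned: Table 2.18 for all data to Week 32, Table 2.20 on-treatment.
2. Present any comparison with the prior 12 months as descriptive, with no significance claim. This covers Table 2.21 and, if they use the same model, Tables 2.23, 2.24 and 2.26.
3. Add a footnote: *The prior-year rate was subject to the entry rule of at least 2 exacerbations; this comparison includes regression to the mean.*
4. Set the pre-period offset to 12 months. The stated offset, treatment time, is undefined before treatment.
5. State whether the prior-year count uses the on-study exacerbation definition (Protocol 7.3.2.4; SAP 10.6.3).

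Optional, if comparable 12-month histories exist: run the same pre/post contrast in historical placebo subjects, parallel to the ACQ-5 benchmark.

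The cost is SAP wording and one footnote. The main fix needs no new data and no new model. The price is a less definitive, and probably less favourable, statement on a secondary endpoint.
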